6.2.5 Spirometry Assessments

Raw spirometry data will be provided by an external data vendor and this data will be used for analyses. The vendor will identify the best value out of 5 attempts at each visit and the best value will be taken for summary and analysis. [REDACTED]

[REDACTED]

[REDACTED]

[REDACTED]

[REDACTED]

[REDACTED]

[REDACTED]

[REDACTED]

[REDACTED]

[REDACTED]

[REDACTED]

[REDACTED]

[REDACTED]

[REDACTED]

[REDACTED]

[REDACTED]

[REDACTED]

[REDACTED]

[REDACTED]

[REDACTED]

[REDACTED]

[REDACTED]

[REDACTED]

6.2.6 GAP Index and Staging System

The GAP index and staging system is a multidimensional prognostic staging system derived from four commonly measured clinical and physiologic variables (Gender, Age and two lung physiology variables (FVC and DLCO)². Points are allocated to each clinical or physiological variable and points are summed to provide a total score (from 0-8). The total score is then used to assign a stage (I, II, or III) as follows:

Confidentiality Statement	
This document is the property of [REDACTED] and may not be duplicated, copied, altered or removed from company without prior approval from [REDACTED] or in compliance with [REDACTED].	

[REDACTED]

GAP Scoring

Predictor	Points Allocated
Gender	Female = 0 Male = 1
Age	≤ 60 = 0 61 – 65 = 1 > 65 = 2
Physiology - FVC, % Predicted	> 75 = 0 50 – 75 = 1 < 50 = 2
Physiology - DLCO, % Predicted	> 55 = 0 36 – 55 = 1 ≤ 35 = 2 *Cannot perform = 3
Total Point Score	0-8

*'Cannot perform' is only assigned if symptoms or lung function prohibited performance of the DLCO maneuver. If DLCO is unavailable for a non-respiratory reason (e.g., an operational reason), the GAP index and staging system cannot be applied.

Staging System

Stage	I	II	III
Points	0-3	4-5	6-8

6.2.7 Study Day

Study day will be calculated as the number of days from first dose of study drug.

- date of event – date of first dose of study drug + 1, for events on or after first dose
- date of event – date of first dose of study drug, for events before first dose

6.2.8 Unscheduled Visits

Only scheduled post-baseline values will be tabulated. Post-baseline repeat / unscheduled assessments will not be summarized but will be listed in the relevant appendices to the CSR.

Controlled Quality Management Document		
	Sponsor:	Pliant Therapeutics Inc.
	Protocol Number:	PLN-74809-IPF-202
STATISTICAL ANALYSIS PLAN. PHASE 2-3-4		

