APPENDIX 1 SCHEDULE OF EVENTS: PARTS B AND C

	Screening	Treatment					EoS / ET
	Visit 1	Visit 2	Visit 3	Visit 4	Visit 5	Visit 6	Visit 7
	Day -28 to Day -1	Baseline Day 1	Week 2 Day 14 (±2 days)	Week 4 Day 28 (±2 days)	Week 8 Day 56 (±3 days)	Week 12 Day 84 (±3 days)	Week 14 Day 98 (±3 days)
Informed consent	X						
Medical history	X						
Demographics (age, sex, race)	X						
██████████	■					■	
Serum pregnancy test	X						
Check inclusion and exclusion criteria	X	X					
Complete physical examination (including height and weight)	X						
Targeted physical examination		X	X	X	X	X	X
Randomization		X					
██████	■	■		■	■	■	■
██████	■						
DLco	X						
██████████	■	■	■	■	■	■	■
Vital signs (post 3 minutes, supine; approx 2 hrs post dose and around the time of the █████)	X	X	X	X	X	X	X
██ ██	■	■	■	■	■	■	■
Hematology (post 8-hour fast)	X	X	X	X	X	X	X
Clinical chemistry (post 8-hour fast) ^f	X	X	X	X	X	X	X
Coagulation (post 8-hour fast)	X	X	X	X	X	X	X
Pharmacokinetic sample plasma × 2 (predose and at least 2 hours postdose) ^g		X		X		X	X ^g
Pharmacokinetic nintedanib/pirfenidone sample plasma x 2 (predose and at least 2 hours post dose to PLN-74809) ^h		X		X		X	X

- [REDACTED]
- g [REDACTED] PLN-74809 levels will be measured. Actual PK sample collection time and dosing time will be recorded. If the participant discontinues the study early, a plasma sample for PK should be taken at the ET Visit if possible.
- h For participants receiving nintedanib/pirfenidone only; timed relative to PLN-74809 dosing.

Week 14 Visit through End of Study

(continued)	Treatment							EoS / ET	
	Visit 7	Visit 8	Visit 9	Visit 10	Visit 11 ^a	Visit 12 ^a	Week 48 / Unscheduled / End of Treatment Visit EoT ^{a,b}	End of Study Visit EoS	
	Week 14 Day 98 (±3 days)	Week 20 Day 140 (±3 days)	Week 24 Day 168 (±3 days)	Week 26 Day 182 (±3 days)	Week 32 Day 224 (±5 days)	Week 40 Day 280 (±5 days)	Final On- Treatment Visit	Final On- Treatment Visit + 2 weeks (±3 days)	
██████████			■						
Targeted physical examination	X	X	X	X	X	X	X	X	
██████	■	■	■	■	■	■	■	■	
██████████	■	■	■	■	■	■	■	■	
Vital signs (post 3 minutes, supine; approx 2 hrs post dose and around the time of the █████)	X	X	X	X	X	X	X	X	
██ ██ ██████	■	■	■	■	■	■	■	■	
Hematology (post 8-hour fast)	X	X	X	X	X	X	X	X	
Clinical chemistry (post 8-hour fast) ^h	X	X	X	X	X	X	X	X	
Coagulation (post 8-hour fast)	X	X	X	X	X	X	X	X	
Pharmacokinetic sample plasma × 2 (predose and at least 2 hours postdose) ^{f, i}			X						

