6.2.3 Baseline

In general, baseline is defined as the last non-missing value (either scheduled, unscheduled or repeat) before the participant receives the first dose of study drug, unless otherwise specified.

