6.2.4 Early Termination Assessments

Early termination assessments will not be summarized. Early termination assessments will appear in the listings as recorded.

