6.15.2 Laboratory Data

Descriptive statistics of the observed values and change from baseline will be presented by treatment group and visit for each continuous hematology, serum chemistry, coagulation, and urinalysis parameter. Shift tables for the change from baseline in categorical parameters will be presented in the natural order of the outcome where possible.

Summaries and listings will be presented using the Système International (SI) unit for each parameter as received from the analytical laboratory.

Each measurement (for continuous data and for categorical data where provided) will be classed as below, within, or above normal range, based on ranges supplied by the laboratory used. Shift tables in relation to the normal range from baseline to each follow-up visit will be presented.

In addition, any confirmed liver abnormalities, identified per Section 6.2.19, will be summarized by treatment group and listed.

All individual laboratory data (including pregnancy testing data) will be listed. Any liver abnormalities identified will be provided as a separate listing.

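### Laboratory and vital-sign summaries use scheduled visits only, so a transient abnormality found between visits may appear in no readable between-group table

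*SAP*

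**What the plan says.** SAP 6.2.8 sets the rule for post-baseline data and gives no exception: "Only scheduled post-baseline values will be tabulated. Post-baseline repeat / unscheduled assessments will not be summarized". The same sentence goes on to send those values to the CSR listings. SAP 6.2.4 adds: "Early termination assessments will not be summarized"; those values are also listed.

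The baseline rule is wider. SAP 6.2.3 takes the "last non-missing value (either scheduled, unscheduled or repeat) before the participant receives the first dose of study drug".

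For laboratory data, SAP 6.15.2 plans descriptive statistics by visit, and "Shift tables in relation to the normal range from baseline to each follow-up visit will be presented". It also plans a by-group summary of confirmed liver abnormalities under 6.2.19, which is redacted. The readable part of SAP 6.15.3 plans vital-sign statistics at each visit.

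Protocol 12.5.1 planned an incidence summary of treatment-emergent laboratory abnormalities by severity and group. SAP section 9, item 6, removes the CTCAE-graded laboratory summaries.

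In the Part D schedule (Protocol Appendix 2) the last on-treatment column is headed "Week 48 / Unscheduled / End of Treatment Visit". Protocol 3.3 describes the same end-of-treatment visit as the scheduled visit that comes next once the last participant reaches 24 weeks. Protocol 3.1 has participants contacted to return for it.

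**The concern.** Extra samples are often taken because something looks wrong. Under these rules a repeat or unscheduled value can set a participant's baseline, but after dosing it cannot show a change in a table. Suppose a participant's creatinine or platelet count is abnormal at a between-visit check and normal again at the next visit. That participant appears as normal in every by-visit shift table. Early termination values, from participants who leave before the end, are also absent from the summaries.

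A by-participant incidence summary would have caught some of this. The graded one was removed, and the readable SAP names no replacement except for the liver.

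Safety and tolerability is the only primary objective, and Part D was added to characterize longer exposure at the highest dose. At stake is whether the tables comparing dose groups with placebo undercount transient abnormalities, and whether the last on-drug value of the longest-exposed participants has a defined place in them.

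**Working it through.** **1. Group sizes.** The plan's figure of about 21 active participants per dose reproduces: 28 × 3/4 = 21 (Part B), 56 × 3/8 = 21 for each Part C dose, and 28 × 3/4 = 21 (Part D). That makes 84 active. Placebo is 7 + 14 + 7 = 28. The plan states no figure for this concern, so the rest is illustrative.

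**2. Visit gaps** (Protocol 3.1 and the schedules of events), in days:
- Parts B/C, visits at Weeks 2, 4, 8, 12: gaps 14, 14, 28, 28; total 84.
- Part D to Week 24, visits at Weeks 2, 4, 8, 12, 14, 20, 24: gaps 14, 14, 28, 28, 14, 42, 28; total 168.
- Part D to Week 48, adding Weeks 26, 32, 40, 48: further gaps 14, 42, 56, 56; total 336.

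**3. Share of excursions touching no scheduled visit.** Assume an excursion of L days that starts uniformly over the treatment period. The missed share is m = Σ max(gap − L, 0) / total days. L is not in the documents, so a range is shown.

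| L (days) | Parts B/C | Part D to Week 24 | Part D to Week 48 |
|---|---|---|---|
| 7 | 56/84 = 67% | 119/168 = 71% | 259/336 = 77% |
| 14 | 28/84 = 33% | 70/168 = 42% | 182/336 = 54% |
| 21 | 14/84 = 17% | 42/168 = 25% | 133/336 = 40% |
| 28 | 0% | 14/168 = 8% | 84/336 = 25% |

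**4. What this means with 21 per dose.** The chance that a table shows at least one case is 1 − (1 − p)^21 if every case counts, and 1 − (1 − p(1 − m))^21 if only scheduled values count. The true risk p is assumed. For Part D to Week 24:

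| p | Every case counted | Scheduled only, L = 7 | L = 14 | L = 21 |
|---|---|---|---|---|
| 10% | 89% | 46% | 72% | 80% |
| 5% | 66% | 27% | 46% | 55% |

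The "every case" column is a ceiling, because it supposes that each excursion is sampled at some point. If only a fraction q of the missed ones is caught by an extra sample, the share that can be tabulated rises from 1 − m to 1 − m(1 − q). The documents do not give q.

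**5. Final On-Treatment Visit.** Assume 28 participants enter evenly over 24 weeks.
- Recalled as soon as the last one reaches Week 24 (Protocol 3.1), each is at week 48 minus entry week. Then 5 of 28 fall in a named window (Weeks 24 and 26 ± 3 days; Weeks 32, 40 and 48 ± 5 days, the last width being assumed).
- Applying the note to Figure 3 in Protocol 3.1, that everyone has a Week 26 visit, the count is 6 of 28.
- On the Protocol 3.3 reading, all 28 fall on a scheduled visit: 9 at Week 48, 9 at Week 40, 7 at Week 32 and 3 at Week 26.

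If a Week 48 final visit were not tabulated, the last on-drug value in the tables would be Week 40 (Day 280), 56 days earlier. The next tabulated value would be the off-drug end-of-study visit at Day 350, a 70-day gap. The missed shares would barely move: 273/350 = 78% for 7 days and 196/350 = 56% for 14 days. The loss would be the last on-drug value itself.

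**The case against.** The strongest reply is that nothing leaves the report. Unscheduled, repeat and early termination values are listed, and SAP 6.15.2 lists all individual laboratory data. Under Protocol 8.7 and 8.8.2, clinically significant or clinically relevant abnormalities are adverse events, and the adverse event tables are not restricted to scheduled visits. The primary endpoint is adverse events; laboratory tests and vital signs are other safety endpoints (SAP 3.1). The study tests no hypothesis. A repeat of an abnormal scheduled value loses nothing, since the scheduled value is already in the table.

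All of that is correct, and it narrows the point to abnormalities found only between visits, or at early termination, that the investigator does not judge clinically significant. It does not remove the point. Protocol 8.7 says that abnormal findings are not adverse events in themselves and usually expects a sign or symptom, so silent peaks depend on judgment. Listings give no between-group comparison.

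Four stronger readings go beyond the documents:
- *The values disappear.* They lose their place in summary tables only.
- *The SAP has no worst-value analysis.* SAP 6.2.16 to 6.2.19, 6.15.4 and the list of tables are redacted, and the end of 6.15.3 cannot be read. The confirmed liver rule may use repeat values. Absence can be stated only for the readable text.
- *The Final On-Treatment Visit is dropped.* This rests on one word in a composite column heading whose footnotes are not readable, and Protocol 3.3 calls the visit scheduled. It is a conflict of labels, not a shown exclusion. Quoting 5 of 28 alone would give only the adverse reading.
- *Between 50% and 88% of excursions are missed.* Those figures come from the longer gaps alone: 1 − 14/28 = 50% and 1 − 7/56 = 88%. A 14-day excursion in a 14-day gap always touches a visit. The schedule-wide shares are the fair ones.

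**Conclusion.** The concern holds in a limited form. As written, the plan can undercount transient laboratory and vital-sign abnormalities in the group comparison, while the listings and the adverse event tables are unaffected. For excursions assumed to last 7 to 14 days, between one third (Parts B/C, 14 days) and about three quarters (Part D to Week 48, 7 days) would touch no scheduled visit. Longer excursions are mostly captured; at 28 days the missed share is 0% in Parts B/C and 8% in Part D to Week 24.

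These shares rest on uniform onset, attendance on nominal days and assumed durations. They bound what a worst-value table could recover, because recovery also needs an extra sample and the frequency of extra sampling is unknown. The loss from excluding early termination values cannot be sized from the documents.

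The status of the Final On-Treatment Visit is an ambiguity to be settled. It matters because SAP 6.2.8 makes tabulation depend on whether a visit counts as scheduled.

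**What to change.** 1. Keep the by-visit tables. For laboratory parameters and vital signs, add a shift from baseline to the worst post-baseline value in each direction, by treatment group, using all scheduled, unscheduled, repeat and early termination values. State this as an exception in SAP 6.2.4 and 6.2.8.
2. Reconcile the Appendix 2 column heading with Protocol 3.3 by stating in SAP 6.2.8 that the Part D Final On-Treatment Visit is tabulated. Show it as a last on-treatment value row with the median and range of exposure, not under a Week 48 label.

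The cost is SAP wording and a few tables from data already collected. Abnormality counts will be somewhat higher, and participants sampled more often have more chances of an abnormal value; a table footnote should say so. SAP section 6 already allows justified additional tables in the study report. Since the SAP log records an addendum after final database lock, tables added now should be labelled as added after lock.

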6.2.9 Conventions for Missing and Partial Dates

All rules explained below for partial / missing dates will be followed unless contradicted by any other data recorded on the electronic Case Report Form (eCRF).

All dates presented in the individual participant listings will be as recorded on the eCRF (i.e., not completed as per the below rules).

6.2.10 Missing / Partial Start / Stop Date of Adverse Events, Medical History and Concomitant Medications

Missing and partial start dates will be imputed solely for the purpose of determining whether an AE is treatment-emergent, medical history is ongoing at Screening, or a medication is concomitant to study treatment.

Partial or missing stop date will be imputed as follows:

If the stop date is completely missing and the event has resolved, or the participant has stopped taking the concomitant medication, the stop date will be imputed as the date of the participant's last clinic visit in the study.

- If only the year is known, the stop date will be imputed as "31-Dec" of that year or as the date of the participant's last clinic visit in the study if in the same year.
- If the month and year are known, the stop date will be imputed as the last day of that month unless the stop date corresponds to the same month as the participant's last clinic visit in which case the date of participant's last clinic visit in the study will be used instead.

Missing start date will be imputed as follows:

- If the stop date occurs on or after the start of study drug or the event / concomitant medication is ongoing, the start date will be imputed as the date of the first dose of study drug.
- If the stop date occurs before the start of study drug, the start date of the event / concomitant medication will be imputed as the participant's screening date or the stop date of the event / concomitant medication whichever the earlier.

Partial start date (year present, but month and day missing)

- If the stop date occurs on or after the start of study drug or the event / concomitant medication is ongoing, and the year is the same as the year of first dosing the start date will be imputed as "01-Jan" of the same year or the date of the first dose of study drug

Confidentiality Statement	
This document is the property of [REDACTED] and may not be duplicated, copied, altered or removed from company without prior approval from [REDACTED] or in compliance with [REDACTED].	

Controlled Quality Management Document		
	Sponsor:	Pliant Therapeutics Inc.
	Protocol Number:	PLN-74809-IPF-202
STATISTICAL ANALYSIS PLAN. PHASE 2-3-4		

whichever is latest. If the year is different from the year of first dosing “01-Jan” will be used.

- If the stop date occurs before the start of study drug, the start date of the event / concomitant medication will be imputed as the “01-Jan” of the same year.

Partial start date (month and year present, but day missing)

- If the stop date occurs on or after the start of study drug or the event / concomitant medication is ongoing, the start date will be imputed as the first day of the same month and year unless this partial start date is in same month as the first dose of study drug in which case the date of first dose of study drug will be used.
- If the stop date occurs before the start of study drug, the start date will be imputed as the first day of the month and year of the partial stop date.

If the start time is missing it will be imputed only in the case where the start date of the concomitant medication / event corresponds to the date of the first dose of study drug. The time will be imputed as the same time as the first dose of study drug. In all other cases the time will not be imputed.

6.2.11 Date of Last Dose of Study Drug

Date of Last Dose will be recorded at the Study Completion/Termination visit, if different from the from Date of Completion/Termination. If Date of Last Dose is not present, the Date of Completion/Termination will be taken as Date of Last Dose for calculation of study drug exposure.

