6.2.12 Exposure to Study Drug

Exposure to study drug will be calculated as follows from the date of last dose (or the date of completion/termination if not present) minus the date of first dose + 1. The exposure calculation will not take into account breaks in therapy.

Duration of exposure (in days) will be calculated as follows:

- Date of Last Dose (or the Date of Completion/Termination if not present) of study drug (irrespective of dose) – Date of First Dose of study drug + 1

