6.2.13 Study Drug Compliance

Study drug compliance will be calculated by comparing the amount of drug dispensed and drug returned for each participant as follows:

QMD [REDACTED]	[REDACTED]
Confidentiality Statement	
This document is the property of [REDACTED] and may not be duplicated, copied, altered or removed from company without prior approval from [REDACTED] or in compliance with [REDACTED].	

[REDACTED]

Controlled Quality Management Document	
	Sponsor: Pliant Therapeutics Inc.
	Protocol Number: PLN-74809-IPF-202
STATISTICAL ANALYSIS PLAN. PHASE 2-3-4	

Number of [REDACTED] = Total dispensed – Total returned (if the number returned is missing, a value of 0 will be used).

Expected [REDACTED] [REDACTED] = Number of days on study (calculated as per Section 6.2.12 for duration of exposure) × [REDACTED] for the relevant study part and dose group (per the table below).

Compliance (%) = (Number of [REDACTED] / Expected number of [REDACTED]) *100

Number of [REDACTED] per study part and dose group

[REDACTED]	[REDACTED]
	[REDACTED]
	[REDACTED]
	[REDACTED]
	[REDACTED]
	[REDACTED]
	[REDACTED]

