6.4 Participant Disposition

Participant disposition will be summarized by treatment group and overall, for the Safety Population as follows:

- The number of participants entering the study.
- The number of participants in each analysis population.
- The number of participants completing study treatment.
- The number of participants not completing study treatment and reason for non-completion of study treatment.
- The number of participants completing the study.
- The number of participants with early termination and the reasons for early termination.
- The reasons for exclusion from the Efficacy Per-Protocol Population will be listed.

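### SAP 6.2.13 counts a missing drug-return count as zero returned, so compliance can only stay the same or be overstated; the completion date used for a blank last-dose date also needs defining

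*SAP*

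**What the plan says.** **Compliance.** SAP 6.2.13 takes the amount used as total dispensed minus total returned, with the convention "if the number returned is missing, a value of 0 will be used". It divides this by an expected amount, which is the daily quantity (redacted) times the "Number of days on study (calculated as per Section 6.2.12 for duration of exposure"), and multiplies by 100. SAP 6.10 summarises the result by treatment group and overall, and lists the compliance and accountability data. Protocol 5.3 requires used and unused medication to be brought back at the scheduled visits. Protocol 5.4 bases compliance on dispensed against returned drug.

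**Last-dose date.** SAP 6.2.11 states: "Date of Last Dose will be recorded at the Study Completion/Termination visit, if different from the from Date of Completion/Termination". If the field is blank, "the Date of Completion/Termination will be taken as Date of Last Dose for calculation of study drug exposure". SAP 6.2.12 puts the same fallback into the exposure formula: "Date of Last Dose (or the Date of Completion/Termination if not present) of study drug (irrespective of dose"). The readable SAP does not say whether this is completion of treatment or of the study. SAP 6.4 counts the two separately: "The number of participants completing study treatment" and "The number of participants completing the study". SAP 6.2.9 adds that the rules for partial and missing dates "will be followed unless contradicted by any other data recorded on the electronic Case Report Form (eCRF").

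**The concern.** A return count that was never recorded is unknown. Entering 0 assumes the most favourable answer, that every unit handed out was swallowed. The protocol expects leftover drug to be returned, so a blank may equally mean that the count was not made or not entered. The error has one direction, and the participants affected could be those with the most drug left over.

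The undefined completion date is a lesser matter of the same kind. The exposure days are also the compliance denominator, so a date that falls after dosing ended would lengthen exposure and lower compliance.

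At stake are the two descriptive tables that tell a reader how much drug stands behind the safety results in each dose group. Safety and tolerability is the primary objective, so these tables should be right. No test or sample-size figure depends on them.

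**Working it through.** **Inputs**
- Parts B and C: 12 weeks of treatment, with Week 12 at Day 84 and the final visit at Day 98 (Protocol 3.3, Appendix 1).
- Final visit: 2 weeks ± 3 days after the last dose (Protocol 3.1), so a gap of 14 days, range 11 to 17.
- Part D: 24 to 48 weeks of treatment plus 2 weeks of follow-up (Protocol 3.3).
- About 21 participants on active drug per dose group (SAP 4).
- The daily unit count is redacted, but it cancels if supply is expressed in days of drug.

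**The schedule reproduces.** 4 + 12 + 2 = 18 weeks, 4 + 24 + 2 = 30 weeks and 4 + 48 + 2 = 54 weeks, as Protocol 3.3 states. Day 98 − Day 84 = 14 days.

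**Missing return count.** Let D be days of drug dispensed, R days' worth returned, and E exposure days. Compliance = 100 × (D − R)/E. Setting R to 0 gives 100 × D/E. The difference is 100 × R/E, which cannot be negative.

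Assume D = E = 84 and u untaken days with no return count. Compliance on a known count is 100 × (84 − u)/84; the reported value is 100%.

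| Untaken days u (assumed) | Overstatement, u/84 | Effect on a mean of 21 |
|---|---|---|
| 7 | 8.3 points | 8.3/21 = 0.4 |
| 14 | 16.7 points | 16.7/21 = 0.8 |
| 28 | 33.3 points | 33.3/21 = 1.6 |

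Overage adds to this. With an assumed 14 extra days dispensed, the reported value is 98/84 = 116.7%, whatever was taken.

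**Completion date, only if it means study completion and nothing on the eCRF overrides it.** Excess per wrongly blank completer:
- Parts B and C: 98 against 84 days, 14/84 = +16.7% (11/84 = +13.1% to 17/84 = +20.2%). Full compliance would read 84/98 = 85.7%.
- Part D minimum, 24-week base (Protocol 3.3): 182 against 168 days, 14/168 = +8.3%; compliance 168/182 = 92.3%.
- Part D minimum, if Week 26 is the end of treatment for the last participant (Protocol 3.1, note to Figure 3): 196 against 182 days, 14/182 = +7.7%; compliance 182/196 = 92.9%. These two protocol passages need to be reconciled.
- Part D at 48 weeks: 350 against 336 days, 14/336 = +4.2%; compliance 336/350 = 96.0%.
- Mean of 21 in Parts B and C: 14/21 = 0.67 day per affected completer.

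**The two together.** They push compliance in opposite directions. With 98 days of drug dispensed, no return count and 98 counted days, compliance reads 98/98 = 100% whatever was taken.

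**The case against.** **On returns.** The protocol does not say what a blank count means. If nothing was left, 0 is the right value. The 7-, 14- and 28-day cases are assumptions, because supply quantities cannot be read. Setting compliance to missing may drop the less adherent participants. No readable analysis population uses a compliance threshold. All of this stands and limits the size of the point. It does not rescue the rule, which assigns one answer to an unknown count. The override in 6.2.9 is no help here, since it concerns dates and not counts.

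**On the date.** A reader might infer that the SAP adds about 14 off-drug days to completers' exposure as a matter of course. The documents do not support that. SAP 6.2.11 requires the last-dose date whenever it differs from the completion date, so by design a blank means the dates are equal. The 14-day error needs four things together: the study-completion reading, a required field left empty, the omission surviving data cleaning, and no overriding eCRF entry. SAP 7 promises full cleaning for Parts A to C. Overriding entries are plausible, for example the Week 12 dosing times that Protocol 7.10 requires on the eCRF. If the date means treatment completion, this error does not arise for completers. What is left is an undefined term.

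Nor do the documents support a reading that the safety results are distorted. Adverse event percentages use the number of participants (SAP 6.3.4), and dates in the listings stay as recorded (SAP 6.2.9).

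**Conclusion.** The missing-return rule in SAP 6.2.13 holds as a minor flaw. Followed exactly, and with exposure days held fixed, it can only leave compliance unchanged or overstate it, and it can produce values above 100% if extra drug was dispensed. The size for one participant depends on the drug left over: 8.3 to 33.3 points over 84 days under the assumed 7 to 28 untaken days, or 0.4 to 1.6 points on a 21-participant mean for each such case. How often the rule fires is unknown, so no claim can be made that the reported compliance is materially wrong. Only the descriptive compliance summary is affected.

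The completion date in 6.2.11 and 6.2.12 is a request for clarification. The 14-day figures are conditional on the reading and safeguards described above. If that error occurred, it would lower compliance and could partly hide the return-count bias.

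**What to change.** **SAP 6.2.13.** Do not replace a missing return count with 0. Set compliance to missing for that participant; the formula uses participant totals, so no interval-level derivation is needed. Report the number affected by treatment group, and keep the zero-return calculation as a sensitivity summary.

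**SAP 6.2.11 and 6.2.12.** State whether the completion date refers to treatment or study. If it is study completion, a completer on schedule always has a different last-dose date, so a blank is an omission. In that case use the latest dosing or drug-discontinuation date documented on the eCRF or, failing that, the last on-treatment visit attended. Flag and count the imputed cases, because the visit fallback can still overstate exposure after an unrecorded early stop.

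**Cost.** A few sentences, a small derivation change, one flag and one extra summary, all from data already collected. The amendment history shows addenda issued up to and after final lock, so a route exists. The price is a few missing compliance values, possibly among less adherent participants, which is why the sensitivity summary is kept.
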